12.1.3.4. Serotype Distribution CAP Population (Secondary Analysis Population)

The Primary Analysis Population will include all events who:

- 1. Participant meets all inclusion and exclusion criteria.
- 2. Event has final diagnosis consistent with CAP.
- 3. Did not receive any pneumococcal vaccination ≤30 days prior to event urine sample collection.
- 4. Event with valid UAD1/2 test results or other pneumococcal serotype result (eg, from bacterial isolate).

Events with same serotype result involving rehospitalisation ≤ 30 days will be considered same event for this analysis.

12.1.3.5. Incidence CAP Population (Exploratory Analysis Population)

The calculation of incidence will include all CAP events identified on the screening log as residents of the hospitals' geographical catchment area either prospectively or retrospectively through ICD discharge code review.

12.1.4. Endpoints

See Section 8 for details of endpoints per study objective.

12.2. Data Management

An electronic database will be created for this study. Details of the database creation are included in the Data Management Plan.

PFIZER CONFIDENTIAL CT45-GSOP-RF152.0 Low-Interventional Study Protocol Template 05-Dec-2019 Page 53 of 70

12.3. Case Report Forms/Data Collection Tools/Electronic Data Record

As used in this protocol, the term CRF should be understood to refer to either a paper form or an electronic data record or both, depending on the data collection method used in this study. A eCRF is required and should be completed for each included subject. The completed original eCRFs are the sole property of Pfizer and should not be made available in any form to third parties, except for authorized representatives of Pfizer or appropriate regulatory authorities, without written permission from Pfizer. The investigator shall ensure that the eCRFs are securely stored at the study site in encrypted electronic and/or paper form and will be password protected or secured in a locked room to prevent access by unauthorized third parties.

The investigator has ultimate responsibility for the collection and reporting of all clinical, safety, and laboratory data entered on the eCRFs and any other data collection forms (source documents) and ensuring that they are accurate, authentic/original, attributable, complete, consistent, legible, timely (contemporaneous), enduring, and available when required. The eCRFs must be signed by the investigator or by an authorized staff member to attest that the data contained on the eCRFs are true. Any corrections to entries made in the eCRFs or source documents must be dated, initialed, and explained (if necessary) and should not obscure the original entry.

In most cases the source documents are the hospital or the physician's chart. In these cases, data collected on the eCRFs must match those charts.

In some cases, thee CRF may also serve as the source document. In these cases, a document should be available at the investigator site and at Pfizer that clearly identifies those data that will be recorded on the eCRF, and for which the eCRF will stand as the source document.

12.3.1. Record Retention

To enable evaluations and/or inspections/audits from regulatory authorities or Pfizer, the investigator agrees to keep records, including the identity of all participating subjects (sufficient information to link records, eg, eCRFs and hospital records), all original signed informed consent [/assent] documents, copies of all eCRFs, safety reporting forms, source documents, detailed records of treatment disposition, and adequate documentation of relevant correspondence (eg, letters, meeting minutes, and telephone call reports). The records should be retained by the investigator according to the International Council for Harmonisation (ICH) guidelines, according to local regulations, or as specified in the clinical study agreement (CSA), whichever is longer. The investigator must ensure that the records continue to be stored securely for so long as they are retained.

If the investigator becomes unable for any reason to continue to retain study records for the required period (eg, retirement, relocation), Pfizer should be prospectively notified. The study records must be transferred to a designee acceptable to Pfizer, such as another investigator, another institution, or to an independent third party arranged by Pfizer.

PFIZER CONFIDENTIAL CT45-GSOP-RF152.0 Low-Interventional Study Protocol Template 05-Dec-2019 Page 54 of 70

Investigator records must be kept for a minimum of 15 years after completion completion or discontinuation of the study or for longer if required by applicable local regulations.

The investigator must obtain Pfizer's written permission before disposing of any records, even if retention requirements have been met.

12.4. Data Analysis

Detailed methodology for summary and statistical analyses of data collected in this study will be documented in a SAP, which will be dated, filed and maintained by the sponsor. The SAP may modify the plans outlined in the protocol; any major modifications of primary endpoint definitions or their analyses would be reflected in a protocol amendment.

12.4.1. Vaccine Effectiveness

If either PCV13 or PPV23 coverage is <10% or >90%, we will assess whether valid VE estimates can be generated for the involved vaccine. If appropriate, we will proceed as follows; odds ratio of having received PCV13 and PPV23 for cases and controls with 95% CI for odds ratio will be calculated. See details on case and control assignment in Section 12.1.1. We will calculate VE as 1-OR x 100. In addition to constructing crude OR and VE estimates, we will perform unconditional logistic regression modelling to assess VE after adjustment for potentially confounding factors. Because of the risk-based approach to catch up vaccination in the over 60 cohort, we will also perform a second adjusted analysis, selecting non-vaccine-type controls similar the VT-serotype cases based on propensity score matching. Further, we will use a two-sided alpha of .025 for all analyses if final VE analysis is not conducted at the interim analysis. If interim analysis is final VE analysis, a two-sided alpha of .05 will be used in the final tables. A second model will be developed excluding immunocompromised persons to evaluate VE without those that may not be able to respond to the vaccine. Only adjusted estimates will be considered the final VE. Time from vaccination will be accounted for in the adjusted analyses. The comparison of the estimates of the effectiveness between PCV13 and PPV23 will be performed using the z-score test. The null hypothesis will be that there is no difference between the two estimates.

For the other study objectives, descriptive analysis will be carried out, presenting the absolute and relative frequencies of the qualitative variables and main measures of centralisation and dispersion in case of quantitative variables. Comparisons between proportions will be performed using χ^2 test, the Fisher's exact test, or the Likelihood Ratio test, as appropriate. For quantitative variables, the Student's t-test or the Analysis Of Variance (ANOVA) test will be used, and when data did not show normality in the Kolmogorov-Smirnov test, the Kruskal-Wallis and Mann-Whitney tests will be used.

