#### 2. INTRODUCTION

This statistical analysis plan (SAP) provides the detailed methodology for summary and statistical analyses of the data collected in Study B1851202. This document may modify the plans outlined in the protocol; however, any major modifications of the primary endpoint definition or its analysis will also be reflected in a protocol amendment. Note that any text taken directly from the protocol is *italicized*, with exceptions note where it appears.

This study is designed to evaluate the effectiveness of 13-valent pneumococcal conjugate vaccine (PCV13) in preventing hospitalised vaccine-type (VT) community acquired pneumococcal (CAP) disease among adults aged ≥60 years in Madrid using a prospective study to collect data for test-negative design (TND) analysis, overall and among immunocompetent persons only. Further this study will also measure the proportion of CAP that is associated with Respiratory Syncitial Virus (RSV) infection.

Pneumococcal vaccination status will be based on whether receipt of ≥1 dose of PCV13 or PPV23 could be confirmed by electronic registries. All available vaccination data will be collected from the registry on subjects and time from vaccination will be incorporated in the analysis phase. Patients will be included regardless of the timing of their vaccination relative to their qualifying pneumonia admission but will be excluded from vaccine effectiveness (VE) and serotype distribution analysis if they received pneumococcal vaccination ≤30 days before hospitalisation for CAP because of risk of false positive urinary antigen detection (UAD) test.

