## 6.1.1.1. Primary Endpoint 1- Main Analysis

## Pneumococcal Vaccination Status for Primary Endpoint

Pneumococcal vaccination status is defined as receipt of ≥1 dose of PCV13 or PPV23 and confirmed by electronic registries. Vaccination status will be categorized as: a) never exposed, b) ever exposed. Ever exposed will be subdivided into: i) exposed <5 years, and ii) exposed ≥5 and <10 years. Persons vaccinated ≥10 years will be considered unexposed.

The Madrid vaccination guidelines (Protocol Table 1) stipulate the timing of PCV13, and we will exclude following participants from the VE analyses:

- Immunocompetent participants who received PCV13 within one year after receiving PPV23
- Immunocompromising participants who received PCV13 within eight weeks after receiving PPV23
- Any participants who received PCV20

Note: Cases and controls include either radiologically confirmed CAP, not radiologically confirmed, or chest radiology not done. If more than 5% of the CAP cases are not radiologically confirmed, then a separate analysis will be performed selecting cases and controls only from the radiologically confirmed CAP cases.

The characteristics of cases and controls will be compared using the chi-square test.

DMB02-GSOP-RF02 5.0 Statistical Analysis Plan Template 05-Dec-2019
PFIZER CONFIDENTIAL
Page 31
TMF Doc ID: 98.03

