For the primary endpoint, the cases will be the patients with CAP in whom PCV13 serotypes are identified by any method and the controls will be the patients with CAP without having VT serotype (even the CAPs for which the serotype was not identified). Multivariable logistic regression model (Appendix 3.3), will be applied to estimate odds of exposure to PCV13 among cases versus controls. All VE estimates will be calculated as  $(1 - \text{odds ratio}) \times 100\%$ . Both unadjusted and adjusted VE will be estimated. Patients' age, sex, study site and the variables deemed to be potential confounders on the basis of prior knowledge (e.g. nationality to be modeled as Spanish vs. non-Spanish; risk level to be modeled as low vs. at-risk vs. high-risk; BMI category to be modeled as obese vs. overweight vs. normal vs. underweight; PSI score as continuous; current drug abuse; antibiotic use within past 14 days; influenza vaccination within the last year; pneumonia in last year [ordinal variable, 0,1,2,3] and PPV23 receipt in past 5 years) will be included in the multivariable regression model for adjustment. Initially, we will employ bivariate models, and only the variables significant at p<.20 in the bivariate models will be included in the final model for adjustment.

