## 6.3.2.1. Exploratory Endpoint 2 - Main Analysis

In this analysis, the VE of PCV13 against VT (PCV13) pneumococcal CAP will be obtained from the primary analysis as described in Section 6.1.1.1. The same method will be used to estimate the VE of PPV23 against VT (PPV23) pneumococcal CAP. The crude difference will then be calculated as:

VE of PCV13 against VT (PCV13) pneumococcal CAP – VE of PPV23 against VT (PPV23) pneumococcal CAP

To evaluate the differences of the effectiveness of these two vaccines, the ORs from both the models that used conditional logistic regression using the propensity matching cases and controls, will be tested using the likelihood ratio and/or z-score test as described in Appendix 3.4.

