#### Appendix 3.3. Calculation of odds ratio

To measure the effectiveness of the PCV13 and PPV23 against the target outcomes, the multivariable logistic regression model will be used Coefficient of the vaccine variable in the model will be exponentiated to estimate the odds ratio. To address the effect of the confounding

DMB02-GSOP-RF02 5.0 Statistical Analysis Plan Template 05-Dec-2019 PFIZER CONFIDENTIAL Page 55 TMF Doc ID: 98.03 variables, the variables that were independently associated with the outcome at p<0.10 in a bivariate analysis will be selected. When selecting the covariates for the final model, the rule of 10 events per covariate (Peduzzi et al 1996) will be followed. The vaccine effectiveness (VE) will be calculated as

VE = 1- adjusted odds ratio  $\times$  100.

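### The plan commits to accounting for time since vaccination in the adjusted VE, but no SAP model says how its dose-age bands enter, and the PCV13–PPV23 comparison is not made at like dose age

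*Protocol*

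**What the plan says.** Protocol 12.4.1 makes the adjusted estimates the final VE and adds: "Time from vaccination will be accounted for in the adjusted analyses". The SAP introduction repeats that "time from vaccination will be incorporated in the analysis phase".

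SAP 6.1.1.1 then sets the exposure categories: "Ever exposed will be subdivided into: i) exposed <5 years, and ii) exposed ≥5 and <10 years". The next sentence is "Persons vaccinated ≥10 years will be considered unexposed".

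The modelling text that follows does not return to the bands. The main logistic regression "will be applied to estimate odds of exposure to PCV13 among cases versus controls". Appendix 3.3 says: "Coefficient of the vaccine variable in the model will be exponentiated to estimate the odds ratio". The matched analyses in 6.1.1.2 also estimate a single PCV13 exposure. Neither the regression covariates nor the propensity-score variables include time since PCV13. The only recency term is PPV23 in the previous five years. SAP 6.5.3 tabulates years since the last dose descriptively.

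For the two-vaccine comparison, SAP 6.3.2.1 uses one VE per vaccine, with PPV23 estimated by the same method as PCV13. "To evaluate the differences of the effectiveness of these two vaccines", the two odds ratios are tested as in Appendix 3.4, whose standard error comes from four exposed/unexposed cells.

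**The concern.** A commitment attached to the final VE has no stated implementation. If protection wanes, a single PCV13 VE is an average over whatever dose ages the enrolled patients have, and that average shifts as the programme ages during enrolment.

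The comparison with PPV23 is more exposed, because programme history gives the two vaccines different dose ages. Adult PPV23 began in 2004, and PCV13 in 2016 for some cohorts. Under Protocol Table 1, adults of 60 and over without risk factors moved from PPV23 to PCV13 in January 2018. A difference between two pooled odds ratios could then reflect the age of the doses and not the vaccines.

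**Working it through.** **1. The plan's own size is for one pooled contrast.** Inputs from SAP 2.2 and Protocol Table 6: control coverage p0 = 0.15, OR = 0.40, ratio r = 1692/170 = 9.95, two-sided alpha 0.025, power 80%, Fleiss with continuity correction.

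- Exposure in cases: p1 = OR·p0 / [1 + p0(OR − 1)] = 0.06/0.91 = 0.0659.
- Mean exposure: (p1 + r·p0)/(r + 1) = 0.1423.
- Uncorrected: n = [2.241·√((r+1)·0.1423·0.8577) + 0.842·√(r·p1·q1 + p0·q0)]² / [r(p0 − p1)²] = (2.592 + 0.724)²/0.0703, about 156.3, rounded up to 157.
- Corrected: (n/4)·[1 + √(1 + 2(r+1)/(n·r·(p0 − p1)))]², about 169.1, rounded up to 170.

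The stated 170 cases are reproduced, for a single exposed/unexposed odds ratio.

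**2. What the 10-year cut-off does.** PCV13 began in adults in 2016 and data collection ends in Q1 2025, so the oldest programme doses are about 9 years old. The rule removes almost no PCV13 doses. It acts mainly on PPV23, in use since 2004.

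**3. Dose age by vaccine.** Enrolment starts in March 2021. Routine PPV23 in adults of 60 and over without risk factors ended in January 2018, so from January 2023 those doses are all at least 5 years old. High-risk patients still receive PPV23 under Table 1, so recent PPV23 doses persist. PCV13 doses from 2018 begin to enter the older band from January 2023.

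**4. Size of a spurious gap.** The documents give neither waning nor dose-age shares, so these are assumptions. For crude odds ratios against a common reference, pooled OR = s·OR(recent) + (1 − s)·OR(older), where s is the share of vaccinated controls dosed less than 5 years ago. If both vaccines wane identically, the gap in pooled VE is (s for PCV13 − s for PPV23) × (VE recent − VE older). With s = 0.7 for PCV13 and 0.3 for PPV23:

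| VE <5 y → 5 to <10 y | Pooled PCV13 | Pooled PPV23 | Gap |
|---|---|---|---|
| 60% → 40% | 54% | 46% | 8 points |
| 70% → 40% | 61% | 49% | 12 points |
| 70% → 20% | 55% | 35% | 20 points |

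A milder 0.6/0.4 mix gives 4 to 10 points, and a stronger 0.8/0.2 mix gives 12 to 30. The gap is zero without waning or with equal mixes. For PCV13 alone under 70% → 40%, pooled VE moves from 61% to 49% as s falls from 0.7 to 0.3.

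**5. The PPV23 covariate.** If the same method is taken literally, PPV23 in the previous five years remains a candidate covariate in the PPV23 model. If it survives the bivariate screen, the PPV23 coefficient describes only doses of 5 to under 10 years, which is then set against a PCV13 estimate pooled over all its doses.

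**6. Precision of band estimates.** Vaccinated cases: 0.0659 × 170 = 11.2. With 30% to 70% of doses in a band and VE 60% in both, a band has 3.4 to 7.8 exposed cases. At an even split (5.6 cases), SE(log OR) = √(1/5.6 + 1/158.8 + 1/126.9 + 1/1438.2) = 0.44, giving a 95% CI for VE of about 5% to 83%. The pooled VE has about 26% to 78%. Power per band, without continuity correction, is 22% to 65% at alpha 0.025 and 35% to 78% at 0.05. The pooled contrast has 84% and 92% by the same formula.

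**The case against.** The bands stand under the heading that defines vaccination status for the primary endpoint, so they may be meant as the exposure variable of the main model. No sentence says they are collapsed, and the Appendix 3.3 wording is generic. This stands in part: a single coefficient is a strong inference from the consistent single-odds-ratio wording and the binary cells of Appendix 3.4, not an explicit exclusion of the bands.

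Dose age is also not ignored. Doses of 10 or more years count as unexposed, vaccination within 30 days is excluded, some PPV23-to-PCV13 intervals are excluded, recent PPV23 is a covariate and propensity variable, and there is a five-year PPV23-naïve analysis. All of this stands. Most of it, however, concerns PPV23, and none of it separates PCV13 doses by age between 30 days and 10 years.

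Finally, the protocol promises to account for time, not to report VE by band. The comparison is exploratory and already uses different serotype sets for the two vaccines, and band-specific intervals will be wide. These points limit the weight of the concern, but they do not supply the missing specification.

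**Conclusion.** The concern holds as a gap between commitment and specification. Time from vaccination is to be accounted for and bands are defined, but no stated model uses them. Apart from a cut-off that hardly touches PCV13, time since PCV13 is not accounted for. This conclusion does not depend on any assumed waning.

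The effect on the PCV13–PPV23 comparison is conditional. It is about 8 to 20 points under the assumed 70%/30% mixes and identical waning, and nil without waning or with equal mixes.

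A reader might infer that the SAP rules the bands out, that the comparison is certainly confounded by dose age, or that all PPV23 doses are old from January 2023. The documents do not support these readings. The SAP is silent on how the bands enter, it gives no waning rates or dose-age shares, and Table 1 keeps PPV23 for high-risk patients. Until January 2023, late PPV23 doses in adults without risk factors could also still be under 5 years old.

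**What to change.** In SAP 6.1.1.1 and Appendix 3.3, add an adjusted model with a three-level exposure: unexposed (never, or 10 or more years ago) as reference, under 5 years, and 5 to under 10 years. Report VE per band, labelled as low-precision estimation, beside the pooled VE, which stays the headline.

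In SAP 6.3.2.1, compare PCV13 and PPV23 within the same band, or standardised to a common dose-age distribution. Take standard errors from the fitted models, because the four-cell formula in Appendix 3.4 reflects neither bands nor adjustment nor matching. In the PPV23 model, drop PPV23 in the previous five years from the covariates and propensity variables, since it duplicates part of the exposure. It can stay in the PCV13 model.

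The cost is SAP wording, one additional model per vaccine, and a revised comparison, using registry dates already collected. The downside is wide intervals: about 11 vaccinated cases in total at 170 cases, and wider still for a within-band comparison of the vaccines. If the sponsor does not want this analysis, the protocol sentence should be amended, so that the two documents agree.

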12.4.2. CAP Incidence Rate

Incidence rates (IR) per 100,000 inhabitants of the study age group will be calculated with their respective 95% confidence intervals.

Numerator: The numerator will include all CAP events – both involving study subjects and other unconsented patients captured on screening log as residents of the hospitals' geographical catchment area. Frequent retrospective review of admissions assigned pneumonia ICD discharge codes will be undertaken monthly to ensure no CAP events are missed from the screening log. Efforts will also be made to assess how many persons from the district were hospitalised for pneumonia outside of the surveillance region.

For SP+CAP, the proportion of CAP events among study subjects with pneumococcus identified by any means, will be multiplied by the calculated CAP incidence rate. For radiologically confirmed CAP, the proportion of CAP events among study subjects that is radiologically confirmed will be multiplied by the calculated CAP incidence rate. Other more complex adjustment processes will also be explored if there is adequate detail captured in the screening log, such as calculation the proportion with pneumococal infection within specific risk/age strata or multiple imputation.

Denominator: Annual population data over 60 years old and estimated person-years data for this age group will be obtained from INE (National Statistical Institute). To determine denominators (catchment area), calculations will be made based on the following parameters: age-specific strata of the total population in the region of Madrid; age-specific strata of total hospital discharges in the region of Madrid; age-specific strata of hospital discharges of the Móstoles (2 hospitals) and Alcorcón (1 hospital). Catchment area is calculated as the proportion of the Móstoles and Alcorcón hospital discharges compared to total hospital discharges in the region of Madrid. These percentages are then applied to the total population of the region of Madrid and hence, catchment population in the Móstoles and Alcorcón hospitals by age group are estimated. If population denominators for adults aged ≥ 60 years are available for underlying at-risk and high-risk medical conditions, incidence will be calculated specifically for these risk groups in aggregate and for individual risk conditions that are of sufficient size as outlined in the SAP.

While every effort will be taken to prospectively and retrospectively capture pneumonia events, incidence estimates will be considered conservative, given established multiple risks for under ascertainment of pneumonia events in studies in this setting (for example, due to misdiagnosis, CXR false negative, or hospitalisation on a different inpatient ward).

